UNIVERSITY OF PENNSYLVANIA**RESEARCH PROTOCOL**

Protocol Title:	Postoperative pain after one-visit root canal treatment on teeth with vital pulps: Comparison of two different root filling techniques
Protocol ID:	825494
Institution:	Department of Endodontics School of Dental Medicine University of Pennsylvania [name] [contact] (office) [contact] (fax) Endodontic Clinic [contact] (main)

Protocol

Objectives

To investigate and compare postoperative pain after one-visit root canal treatment (RCT) on teeth with vital pulps using two different obturation techniques.

Background

In the past, different obturation techniques have been compared. The study listed below compared 2 different techniques with significant findings. The most current technique used, single cone with bioceramic sealer, has not been compared. Our project will compare the postoperative pain of this technique to another common technique used in our clinic.

Postoperative pain after one-visit root-canal treatment on teeth with vital pulps: Comparison of three different obturation techniques Med Oral Patol Oral Cir Bucal. 2012 Jul 1;17

(4):e721-7. Luis-O. Alonso-Espeleta, Carmen Gasco-Garcia, Lizett Castellanos-Cosano, Jenifer Martín-González, Francisco-J. López-Frías, Juan-J. Segura-Egea

Study Design and Ethics

This prospective clinical trial was reviewed and approved by the institutional review board (Protocol ID: 827968). Our study will be a non-randomized clinical trial. Patients will sign a dental consent for prior to treatment. Patients participation in the study is voluntary. We will perform our normal diagnostic tests to determine the need for root canal treatment and the vitality of the tooth. Only vital teeth will be included in this study. Once we have determined need for root canal therapy, we will determine if it can be done in one visit. One month we will use the warm vertical/AH+ sealer, the next month will use single cone/ bioceramic sealer to obturate these teeth. Patients will be asked to complete a pain scale questionnaire before treatment and at 4, 24, and 48 hours after completion of treatment. Patient's names, insurance, and medical information will not appear on the forms, only a chart number. The patients will receive a pre-stamped, pre-addressed envelope to return the surveys. The sample size was calculated based on a type I error of 0.05 and the power of 80%. The minimum sample size was determined to be 50 patients in each group. We will increase the number to compensate the possibility of losing follow-up (Graunaite et al., 2018).

Study duration

The subjects were recruited for the study from November 2016 to May 2018 during the planned eighteen-month period at the Department of Endodontics.

Subject enrollment and inclusion/exclusion criteria

The study was performed on teeth with vital pulps in patients at least 18 years old.

Consecutive patients presenting to the Department of Endodontics for routine root canal treatment were recruited for the study.

Inclusion criteria:

Diagnosis of asymptomatic or symptomatic irreversible pulpitis according to AAE consensus. The diagnosis was based on clinical examinations and confirmed upon accessing the teeth. Non-contributory medical history (ASA Class I & II) Consenting adults age 18 years and older Included patients were given oral and written information agreed for participation and signed the informed consent Record of detailed clinical examinations, including but not limited to percussion/palpation testing and periodontal probing.

Exclusion criteria:

Non-consenting patients and patients below 18 years of age
Medical history with ASA Class III & IV
Non-restorable teeth
Teeth with a non-vital pulp
Periapical radiolucency showed on the radiographs
Periodontal probing depths were more than 4mm
Pre-medication with antibiotics and/or analgesics 24 hours before the treatment
Patients taking analgesics routinely for non-dental reasons

Treatment Protocol

Patients will present to the endodontic clinic as needed. If a patient is determined to have a diagnosis of irreversible pulpitis, then they will be asked if they would like to participate in the study. If a patient chooses not to participate, they will proceed with their root canal treatment as needed. If a patient agrees to participate, they will be asked to sign a consent form for participation. Patients will be given a questionnaire to complete regarding pain before the procedure. At that point, an endodontic resident will perform the root canal treatment and fill the root canal with one of the two techniques scheduled that month. At the end of treatment, the patient will be given a survey to fill out asked to fill out the survey at 4, 24, and 48 hours after the completion on treatment. The survey will be a pain questionnaire on a Visual Analog scale (see attached) concerning their level of pain following root canal treatment. Patients are typically given a 6 month follow up after root canal treatment, however, there will be no follow up concerning our study.

Statistical Analysis

We compared the VAS scores between the root canal filling techniques using chi-square or two-way ANOVA to explore the differences between the groups. Changes in outcome variables over time were compared by generalised estimating equation (GEE) analysis, which allows for correlation within repeated observations per individual (Liang and Zeger, 1986). Statistical analysis of the data was performed with IBM SPSS Statistics Version 23 (IBM Corp, Armonk, NY). Statistical significance was set at 0.05 level.

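### The month's technique is fixed before patients are judged suitable, invited and confirmed eligible; nothing conceals it, and no count by technique is planned of eligible patients not entered

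*Combined protocol and SAP*

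**What the plan says.** - **Design** (Study Design and Ethics): "Our study will be a non-randomized clinical trial".
- **Allocation** (same section): "One month we will use the warm vertical/AH+ sealer, the next month will use single cone/ bioceramic sealer to obturate these teeth". Treatment Protocol repeats this: the resident is to "fill the root canal with one of the two techniques scheduled that month".
- **One-visit judgement** (Study Design and Ethics): "Once we have determined need for root canal therapy, we will determine if it can be done in one visit".
- **Invitation** (Treatment Protocol): after the diagnosis, "they will be asked if they would like to participate in the study". Consent and the pre-treatment pain questionnaire follow.
- **Those who decline** (Treatment Protocol): "If a patient chooses not to participate, they will proceed with their root canal treatment as needed".
- **Recruitment** (Subject enrollment and inclusion/exclusion criteria): "Consecutive patients presenting to the Department of Endodontics for routine root canal treatment were recruited for the study". The inclusion criteria add that the diagnosis is confirmed when the tooth is opened.

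No section says that the monthly schedule is withheld from those who diagnose, invite or treat. None provides for a count of patients who were eligible, judged unsuitable for one visit, asked, declined or dropped on access.

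**The concern.** When the allocation is known before a patient is entered, the decision to enter can depend on it. Staff who expect a difficult or painful case may, without intending to, be readier to enter that patient in one technique's months than in the other's. The two groups then differ in who they contain, and a difference in postoperative VAS could appear or be hidden with no effect of technique. This is a separate route from season or operator, because it acts through entry to the study. Adjustment for pre-treatment VAS and diagnosis would remove only what those two variables capture, and the Statistical Analysis section names no such adjustment.

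**Working it through.** **Order of events.** The documents give this sequence:
1. The calendar month fixes the technique.
2. The patient presents and is diagnosed.
3. Staff judge whether one visit is enough.
4. The patient is invited and consents or declines.
5. The pre-treatment VAS is completed.
6. The diagnosis is confirmed on access.
7. The canals are filled with that month's technique.

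Steps 2 to 6 all follow step 1. Steps 3, 4 and 6 each decide whether a patient is in the study. Consecutive recruitment governs who is approached in step 4. It does not govern steps 3 and 6, or the patient's reply in step 4.

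**The plan's own figure.** The minimum is 50 per group at 5% type I error and 80% power. It cannot be reproduced, because no effect size, SD or sidedness is given. Solved backwards, two-sided, the detectable difference is (1.960 + 0.842) × √(2/50) = 0.560 SD by the normal approximation and 0.566 SD by the t distribution. If the 5% is one-sided it is about 0.50 SD. The yardstick used below is 0.566 SD.

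**Illustration (all inputs assumed).** Expected pain is normal. In one technique's months only, a share k of the top third (q = 1/3) is not entered. The cut-off is z = 0.431, with normal density φ(z) = 0.364. The mean expected pain of those entered shifts by −k·φ(z)/(1 − k·q):
- k = 0.2: 0.2 × 0.364/0.933 = 0.078 SD lower
- k = 0.3: 0.3 × 0.364/0.900 = 0.121 SD lower
- k = 0.5: 0.5 × 0.364/0.833 = 0.218 SD lower

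The shift in actual postoperative VAS is this figure times r, the correlation between expected and actual pain. r = 1 means that staff predict perfectly, so it is the ceiling. The chance of a significant result with no true effect, at 50 per group and a two-sided 5% z-test, is Φ(b/0.2 − 1.96) + Φ(−b/0.2 − 1.96), where b is the shift in SD and 0.2 = √(2/50).

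| Share of top third not entered | Shift, r = 1 | Shift, r = 0.3 to 0.5 | Shift as % of 0.566 SD: r = 1; r = 0.3 to 0.5 | False-positive rate: r = 1; r = 0.3 to 0.5 |
|---|---|---|---|---|
| 20% | 0.078 | 0.023 to 0.039 | 14%; 4 to 7% | 6.8%; 5.2 to 5.4% |
| 30% | 0.121 | 0.036 to 0.061 | 21%; 6 to 11% | 9.3%; 5.4 to 6.1% |
| 50% | 0.218 | 0.065 to 0.109 | 39%; 12 to 19% | 19.3%; 6.2 to 8.5% |

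The documents give no value for k or r, and nothing to show that either technique's months attract this behaviour.

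**The case against.** The protocol openly calls the trial non-randomised and specifies consecutive recruitment. Several criteria leave little discretion: ASA class, probing depth, radiolucency and premedication. Pre-treatment VAS and a record of the clinical examination are collected, so gross selection on pain or diagnosis would show in a comparison by technique. No reason is given why staff would treat painful cases differently by technique. Recruitment is reported in the past tense, November 2016 to May 2018, so a change of allocation may come too late.

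Much of this stands. It limits the size of the problem and where the remedy can apply. It does not close the route: declaring the design is not a safeguard, consecutive approach leaves the one-visit judgement, consent and confirmation on access open, and the pre-treatment VAS shows only selection that acts through measured pain.

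Four stronger readings are tempting, and the documents do not support them:
- **Staff steered bookings near a month end.** No booking procedure is described; patients present as needed.
- **Patients chose to consent knowing the technique.** The documents do not say whether they were told.
- **Selection could be neither prevented nor detected.** Consecutive recruitment gives partial prevention, and the baseline VAS gives partial detection.
- **The consecutive claim is false.** It is undocumented in this plan, which is different.

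**Conclusion.** The concern holds as a weakness of design: following the monthly schedule as written leaves entry open to selection by technique, with no concealment and no planned flow count to show whether it happened. That staff know the technique is an inference, from a schedule that the treating residents carry out and that nothing withholds from them. Under the assumed model the bias is small to moderate: at most 0.08 to 0.22 SD, and 0.02 to 0.11 SD at correlations of 0.3 to 0.5, against about 0.57 SD detectable. These figures rest on a normal distribution, selection confined to the top third in one technique's months, and a two-sided 5% test with exactly 50 per group. They show what could happen and do not estimate what did. The point should be addressed, and it does not by itself invalidate the comparison.

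**What to change.** **For any patient not yet entered.** Replace the monthly schedule with individual allocation from a pre-prepared, randomised, sealed and numbered envelope. Open it after consent, pre-treatment VAS and confirmed vitality, when the canals are ready to fill. Record the technique actually used, and analyse by the technique allocated. Cost: both filling kits must be available every day, with a small risk of mix-ups. No extra patients are needed.

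**For patients already treated under the monthly schedule.**
- Compare pre-treatment VAS and diagnosis by technique, and adjust the comparison of techniques for both.
- Report the flow by technique as far as records allow: eligible, unsuitable for one visit, asked, declined, dropped on access. Say which counts are unavailable; charts may not record who was asked or refused.
- State possible selection by technique as a limit on the conclusion.
- Do not use a difference in entry proportions alone as the test of whether recruitment was consecutive. Chance or voluntary refusal can produce a difference, and equal proportions can hide a different case mix.

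Cost: a search of clinic records, which may need ethics review where it covers patients who did not consent, and a small change to the analysis.

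### The treating resident is absent from the stated analysis, so any difference in resident mix between the two sets of alternating months could be read as a technique effect

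*Combined protocol and SAP*

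**What the plan says.** All references are to the combined protocol and SAP.

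- **Operator.** The Treatment Protocol section states that "an endodontic resident will perform the root canal treatment and fill the root canal with one of the two techniques scheduled that month". It does not say how many residents took part, how patients were assigned to them, or how their technique was standardized.
- **Allocation.** Study Design and Ethics says "Our study will be a non-randomized clinical trial" and sets the technique by month: "One month we will use the warm vertical/AH+ sealer, the next month will use single cone/ bioceramic sealer to obturate these teeth".
- **Period.** Under Study duration, "The subjects were recruited for the study from November 2016 to May 2018 during the planned eighteen-month period".
- **Analysis.** The Statistical Analysis section says "We compared the VAS scores between the root canal filling techniques using chi-square or two-way ANOVA to explore the differences between the groups". The second ANOVA factor is not named. Changes over time are analysed by GEE, "which allows for correlation within repeated observations per individual". No operator term and no clustering by operator is mentioned.

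**The concern.** The comparison is meant to isolate the filling technique, but the resident also performs everything that precedes the filling, and those steps may affect postoperative pain. Without randomization, a resident's split between the two techniques depends on the months in which that resident saw study patients.

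Bias needs two conditions together: residents' shares of patients differ between the two groups, and residents differ in the pain their patients report. The stated analysis would then credit the operator difference to the technique, with a standard error that ignores operator variation. Unequal total caseloads are not enough. A resident who treats many patients, but the same share of each group, adds no bias.

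**Working it through.** **The plan's own figure.** Study Design and Ethics gives a minimum of 50 per group at type I error 0.05 and 80% power, without an effect size, SD or sidedness. It can only be solved backwards, here for a comparison of means: d = √(2/50) × (z_alpha + z_power).
- Two-sided: 0.20 × (1.960 + 0.842) = 0.56 SD.
- One-sided: 0.20 × (1.645 + 0.842) = 0.50 SD.

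The figure can be neither confirmed nor refuted. The 0.56 SD serves below only as a yardstick.

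**Assumed inputs (not in the documents).** 10 residents; operator ICC 0.05 to 0.10; 50 patients per group, the stated minimum.

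**Formula.** Let p_i1 and p_i2 be resident i's share of the patients in each group, and S = Σ(p_i1 − p_i2)². In units of the outcome variance,

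Var(difference) = ICC × S + (1 − ICC) × 2/50,

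against a nominal 2/50 = 0.04. With R the ratio of the two, test size ≈ 2 × P(Z > 1.96/√R).

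**Imbalance of 75:25.** Five residents treat 75% of one group and 25% of the other, and the other five the reverse. Each resident's shares are 0.15 and 0.05, so S = 10 × 0.10² = 0.10.
- ICC 0.05: 0.005 + 0.038 = 0.043; R = 1.075; size 5.9%.
- ICC 0.10: 0.010 + 0.036 = 0.046; R = 1.15; size 6.8%.

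**Imbalance of 2:1**, as when a resident is present for three consecutive months with an even monthly caseload. Shares are 2/15 and 1/15, so S = 10 × (1/15)² = 0.044.
- ICC 0.05: 0.0022 + 0.038 = 0.0402; R = 1.006; size 5.1%.
- ICC 0.10: 0.0044 + 0.036 = 0.0404; R = 1.011; size 5.1%.

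**Equal shares.** S = 0, so R = 0.95 to 0.90. There is no bias; leaving operator out only loses a little precision.

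**Typical spurious difference at 75:25.** √(ICC × S) = √0.005 to √0.010 = 0.07 to 0.10 SD, which is about 13% to 18% of the 0.56 SD yardstick.

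**Second calculation, with a fixed gap between two types of operator.** Bias = (gap in SD) × (difference between groups in the share treated by one type), with 50 per group. Two-sided test size:

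| Operator gap | Equal shares | 10 points | 20 points | 40 points |
|---|---|---|---|---|
| 0.3 SD | 5.0% | 5.3% | 6.0% | 9.2% |
| 0.5 SD | 5.0% | 5.7% | 7.9% | 17.0% |
| 0.8 SD | 5.0% | 6.9% | 12.6% | 36.0% |

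**Simulation** (6 or 12 residents, ICC 0.05 or 0.10, 4,000 runs per setting). The unadjusted t-test had type I error 0.044 to 0.054 when expected shares were equal, and 0.052 to 0.095 when shares were drawn separately for each group. With resident as a fixed effect it was 0.042 to 0.057 throughout.

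**The case against.** The strongest reply is that the design already does much of the balancing. Under monthly alternation, a resident present without a break has technique months that differ by at most one: 6:6 over 12 months, 2:1 over 3. Slow gains in skill fall on both techniques. A 75:25 split is more uneven than continuous attendance would give unless monthly caseloads vary, and even then the test size stays below 7%. This stands, and it is why the expected effect is modest. It is not a guarantee, because attendance and caseload by month are not controlled. Moreover, 12 is even, so strict alternation gives a calendar month the same technique each year. November to May falls in the window twice, and any schedule tied to those months would recur with the same technique.

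The second ANOVA factor is also unnamed, so operator is unstated rather than excluded. That is fair, but an unnamed factor cannot be credited as operator adjustment. If resident was intended, saying so settles most of the point.

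It may also be said that this is only one route of the disclosed weakness of allocation by month. That is largely right. It merits its own line because it has its own remedy: adjusting for baseline pain would not remove operator differences, and adjusting for month would not reliably do so.

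A reader might infer more: that resident imbalance did bias this trial, or that the error rate reaches 10% to 16%. The documents support neither. They record no imbalance, caseload or turnover. The 10% to 16% figure needs every resident to use only one technique (S = 0.40; R = 1.45 to 1.90), which would mean absence from study treatment in every other month. A 5 mm spurious difference might likewise be inferred from a 10 mm gap between two halves of the residents at 75:25 (0.5 × 10). With ICC 0.05 to 0.10, that gap has a standard deviation of √(0.4 × ICC) = 0.14 to 0.20 SD, or 3.5 to 5.0 mm if the VAS SD is 25 mm (assumed). A gap of 10 mm would then be 2 to 2.8 standard deviations. The typical spurious difference is about 1.8 to 2.5 mm.

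**Conclusion.** The point holds as a conditional one. Residents perform the whole treatment, the technique follows the calendar without randomization, and the stated analysis names no operator term. Nothing in the analysis as written would separate a difference in resident mix from a difference in technique.

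Whether such a difference exists, and how large its effect is, cannot be told from the documents. Under the ICC assumptions the inflation ranges from negligible at 2:1 to 5.9% to 6.8% at 75:25. The larger values in the table need both a wide gap between operators and a wide imbalance. None of these is an estimate for this trial. The point justifies a cheap change to the analysis and does not by itself discredit the comparison.

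**What to change.** 1. Record a code for the treating resident for each study tooth. The forms carry a chart number, so this is a chart look-up, assuming that the chart identifies the operator; the documents do not say so.
2. Tabulate cases per resident by technique. This shows directly whether an imbalance exists.
3. Include resident in the model-based comparison of VAS scores, as a fixed effect, or as a random effect if there are many residents with few cases each. State this in the Statistical Analysis section and name the second ANOVA factor. The chi-square option cannot carry the adjustment.
4. Report the technique difference with and without resident in the model.

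**Cost.** No patient contact and no design change. With 10 residents and 50 per group, fixed effects use 9 of 98 residual degrees of freedom and leave on average 5 cases per resident and technique. Residents who used only one technique contribute little to the within-resident contrast, and if all did so it could not be estimated; the table in step 2 would show this.

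### The technique comparison specifies no adjustment for preoperative pain, although that pain is recorded and technique follows alternating months without randomisation

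*Combined protocol and SAP*

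**What the plan says.** The Statistical Analysis section gives two analyses. For technique: "We compared the VAS scores between the root canal filling techniques using chi-square or two-way ANOVA to explore the differences between the groups". For time: "Changes in outcome variables over time were compared by generalised estimating equation (GEE) analysis", with allowance for within-patient correlation. No covariate, second ANOVA factor or GEE term is named, and nothing says how the preoperative score is used.

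On design, Study Design and Ethics states: "Our study will be a non-randomized clinical trial". It sets allocation by calendar: "One month we will use the warm vertical/AH+ sealer, the next month will use single cone/ bioceramic sealer to obturate these teeth". The Treatment Protocol agrees that residents "fill the root canal with one of the two techniques scheduled that month".

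On data, Study Design and Ethics says: "Patients will be asked to complete a pain scale questionnaire before treatment and at 4, 24, and 48 hours after completion of treatment". The Treatment Protocol confirms the preoperative form: "Patients will be given a questionnaire to complete regarding pain before the procedure". The visual analogue scale is mentioned only for the postoperative form: "The survey will be a pain questionnaire on a Visual Analog scale (see attached) concerning their level of pain following root canal treatment".

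**The concern.** The objective is to compare postoperative pain between two filling techniques, with at least 50 patients in each group. Pain before treatment is an obvious candidate predictor of pain afterwards. The inclusion criteria admit both asymptomatic and symptomatic irreversible pulpitis, so preoperative pain may vary a good deal between patients. A predictor that is collected but left out of the comparison costs precision that no extra patients would be needed to recover.

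The second issue is bias. Scheduling technique by month in consecutive patients limits the choice of technique for an individual patient, but it does not give the balance in expectation that randomisation gives. If preoperative pain differed systematically between the two sets of months, an unadjusted contrast would attribute part of that difference to technique.

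**Working it through.** **Inputs from the documents.** Type I error 0.05, power 80%, minimum 50 per group (Study Design and Ethics); significance level 0.05 (Statistical Analysis); a planned eighteen-month recruitment period (Study duration). No SD, effect size, response rate, sidedness or pre/post correlation is given.

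**The plan's own figure.** The 50 per group cannot be reproduced without an effect size. It was back-solved instead. By the normal approximation, two-sided, d = √(2/50) × (1.960 + 0.842) = 0.2 × 2.802 = 0.560 SD. With the noncentral t distribution on 98 df, d = 0.566 SD. A comparison of 50% with 23% fits about as well (49 per group without continuity correction, 56 with it). The figure is neither confirmed nor refuted; d = 0.566 serves only as a yardstick.

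**Precision.** Let r be the assumed correlation between preoperative and postoperative pain. Adjustment reduces the residual SD by the factor √(1 − r²). Power is evaluated at 0.566/√(1 − r²) on 97 df. The 95% CI half-width is t(97) × √(0.04 × (1 − r²)) in SD units, where 0.04 = 2/50.

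| r | Power | CI half-width (SD) | Narrower by |
|---|---|---|---|
| 0 | 80.0% | 0.397 | – |
| 0.1 | 80.4% | 0.395 | 0.5% |
| 0.2 | 81.6% | 0.389 | 2% |
| 0.3 | 83.6% | 0.379 | 5% |
| 0.5 | 89.9% | 0.344 | 13% |
| 0.6 | 93.8% | 0.318 | 20% |

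The difference detectable with 80% power falls from 0.566 SD to about 0.540 SD (r = 0.3) or 0.453 SD (r = 0.6).

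**Bias, if preoperative pain differs systematically by D SD between the two sets of months.** The unadjusted contrast shifts by D × r. The two-sided false-positive rate follows from the noncentral t distribution.

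| D | Shift, r = 0.3 | Rate | Shift, r = 0.6 | Rate |
|---|---|---|---|---|
| 0.1 | 0.03 SD | 5.3% | 0.06 SD | 6.0% |
| 0.2 | 0.06 SD | 6.0% | 0.12 SD | 9.1% |
| 0.3 | 0.09 SD | 7.3% | 0.18 SD | 14.5% |

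In simulation at D = 0.3 the adjusted test rejected at 5.0% and 5.1%.

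**Without a systematic difference.** Under chance imbalance alone, the simulated unadjusted rate was 4.9% and 5.1% for r = 0.3 and 0.6. If preoperative pain clusters by month, assume eighteen months, nine per technique, hence 50/9 = 5.56 patients per month. The design effect is 1 + (5.56 − 1) × ICC × r². At an assumed ICC of 0.05 this is 1.021 (r = 0.3) and 1.082 (r = 0.6), giving about 5.2% and 6.0%. Conditional on one fixed observed imbalance of 0.3 SD, the rate is about 6% to 9%.

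**Price of adjusting.** An observed imbalance of D multiplies the adjusted variance by 1 + [D²/(2 × 49)]/(2/50): 1.0% more at D = 0.2, 2.3% at 0.3 and 6.4% at 0.5. At D = 0.5, net power is 77.9% (r = 0.1), 79.2% (r = 0.2), 81.3% (r = 0.3) and 92.4% (r = 0.6).

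These figures are for a continuous score. They do not carry over directly if the VAS is categorised for a chi-square test.

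**The case against.** The strongest reply is that the plan is underspecified rather than wrong. Pain is measured at four times, one of them before treatment, and the GEE is said to address change over time. A reader could take the preoperative score as the first time point, in which case a technique-by-time term would already use it. The unnamed ANOVA factor could also be a preoperative pain category. This stands as a possible reading, but it is stated nowhere, and a score entered as one more time point is not the same as a postoperative contrast adjusted for it.

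The bias argument is conditional. Consecutive recruitment and monthly alternation limit patient-level selection and spread seasonal drift over both techniques, and the documents show no difference in preoperative pain between months. That is right, and it is why precision carries the case.

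The precision gain is conditional too. With r unknown it may be under 2 percentage points of power, and with a large imbalance and a weak correlation there is a small loss.

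The uncorrected GEE sandwich test is slightly liberal with 100 patients. In simulations with an assumed correlation of 0.5 between scores it rejected at 5.6%–5.8% under no effect, against about 5% for a model-based t test. This is minor, applies to a method the plan already uses, and can be avoided.

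Finally, recruitment and analysis are described in the past tense, so the change may only be possible as a post hoc analysis. That limits its value as pre-specification, but not the usefulness of the adjusted estimate.

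**Conclusion.** The concern holds as an inexpensive improvement, with medium confidence. Preoperative pain is recorded, technique is allocated by month without randomisation, and no adjustment for that pain is specified.

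The supported gain is precision: about 4 to 14 percentage points of power for r between 0.3 and 0.6, and little or nothing at r of 0.2 or less. In the unfavourable case (r of 0.2 or less with a 0.5 SD imbalance), power is 1 to 2 points below the nominal 80%. Protection against bias is a secondary gain that depends on a systematic difference between months, for which there is no evidence. All sizes rest on assumed correlations and on an effect back-solved from a two-sided t test that the documents do not say was used. Nothing here shows that imbalance occurred or that the trial's result is invalid.

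**What to change.** Make the main technique comparison one GEE or linear mixed model of the 4, 24 and 48 hour scores, and write into the Statistical Analysis section:

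- **Terms:** technique, time, technique by time, and the preoperative pain score as a covariate, once the scale of the pre-treatment form has been confirmed.
- **Main contrast:** state which one it is, for example the technique difference averaged over the three times.
- **Inference:** use the mixed model or a model-based t test, or a small-sample correction if the GEE sandwich variance is kept.
- **Reporting:** give the adjusted difference with its 95% CI beside the unadjusted result, and tabulate preoperative pain by technique.
- **ANOVA:** if the two-way ANOVA stays, name its second factor.
- **Diagnosis:** add symptomatic or asymptomatic status as a covariate or sensitivity analysis only if it can be retrieved from the chart.
- **Limits:** say that confounding by month, operator and unmeasured factors remains.
- **Timing:** if the data have already been analysed, label this model post hoc and report it beside the analysis already done.

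**Cost.** No new data collection is needed for preoperative pain, provided the form yields a usable score. Patients without that form need a stated handling rule. Diagnosis would need linkage through the chart number; the requirement for recorded clinical examinations makes this plausible, but the documents do not establish it. A single pain rating is imperfect: at an assumed reliability of 0.8, 20% of any systematic bias remains (0.3 × r × 0.2 = 0.018 SD at r = 0.3 and 0.036 SD at r = 0.6, for a 0.3 SD difference).
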